2. An Adverse Device Effect
3. An Adverse Event occurring in association with a study procedure
4. Hypoglycemia meeting the definition of severe hypoglycemia as defined below
5. Diabetic ketoacidosis (DKA) as defined below (#4) or in the absence of DKA, a hyperglycemic or ketosis event meeting the criteria defined below

Relationship of Adverse Event to Study Device

The study investigator will assess the relationship of any adverse event to be related or unrelated by determining if there is a reasonable possibility that the adverse event may have been caused by the study device.

To ensure consistency of adverse event causality assessments, investigators should apply the following general guideline when determining whether an adverse event is related:

- Yes. There is a plausible temporal relationship between the onset of the adverse event and the study intervention, and the adverse event cannot be readily explained by the participant's clinical state, intercurrent illness, or concomitant therapies; and/or the adverse event follows a known pattern of response to the study intervention; and/or the adverse event abates or resolves upon discontinuation of the study intervention or dose reduction and, if applicable, reappears upon re-challenge.
- No. Evidence exists that the adverse event has an etiology other than the study intervention (e.g., preexisting medical condition, underlying disease, intercurrent illness, or concomitant medication); and/or the adverse event has no plausible temporal relationship to study intervention.

Intensity of Adverse Event

The intensity of an adverse event will be rated on a three-point scale: (1) mild, (2) moderate, or (3) severe. It is emphasized that the term severe is a measure of intensity; thus, a severe adverse event is not necessarily serious. For example, itching for several days may be rated as severe, but may not be clinically serious.

- MILD: Usually transient, requires no special treatment, and does not interfere with the participant's daily activities.
- MODERATE: Usually causes a low level of inconvenience or concern to the participant and may interfere with daily activities but is usually ameliorated by simple therapeutic measures.
- SEVERE: Interrupts a participant's usual daily activities and generally requires systemic therapy or other treatment.

Reportable Device Issues

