- All unexpected adverse device events, (UADEs), ADEs, device complaints, and device malfunctions will be reported irrespective of whether an adverse event occurred.

Criteria for Discontinuation of Individual Participants:

Subjects can decide to discontinue entirely from the study at any time for any reason. This is documented as withdrawal of consent. Subjects can also be discontinued from the study or discontinued from the study treatment due to Investigator or Sponsor decision as detailed below.

1. Withdrawal of consent.
2. At the Investigator's discretion in certain situations such as lack of compliance or serious adverse event. (A single severe hypoglycemic event resulting in seizure or LOC or DKA).
3. 2 or more hypoglycemic events based on CGM readings that do not correlate with standard finger stick blood glucose monitor readings.
4. One DKA event or one episode of hyperglycemic, hyperosmolar nonketotic syndrome (HHNS).
5. Skin infection at the site of device insertion that occurs after placement of the device.
6. Transfer of the patient to the ICU or deterioration of medical condition that in the judgment of the principal investigator carries an unacceptable risk for the participant.
7. Skin irritation at the site of device insertion prompting the patient to request removal of the device.

Criteria for stopping the overall study:

1. The IRB will have the responsibility of determining if the overall study should be stopped. Each participant withdrawal (except withdrawal of consent) will be reported to the IRB within 3 days.
2. If an investigational device malfunction results in an SAE and the issue cannot be corrected by a modification to the system or a component of the system or adjustment to protocol procedures, the study will be stopped.
3. In the case of unanticipated adverse device effects (UADEs) related to a severe adverse event, the study will be stopped while the severe adverse event is evaluated and a root cause is determined by the Sponsor.

Randomization:

Patients that meet enrollment eligibility and consent to participate in the RCT will be randomized 1:1 to one of two groups, treatment or control using Research Electronic Data Capture (REDCap).

Randomization will be performed by assigning computerized random numbers. Computerized random numbers will be generated by statistical software.

Application of the Dexcom Devices:

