Glucose management of patients in the treatment group will be guided by readings from the Dexcom G6. The Dexcom device will provide interstitial fluid glucose measurements at five-minute intervals used to construct a graph for trending CGM levels as well as an approximate rate of change. Threshold alarm for hypoglycemia will be set with CGM glucose values < 100 mg/dL and system alarm for CGM glucose value < 55 mg/dL. The alarms will be incorporated into the decision protocol for treatment of low blood glucose levels to achieve the stated goal of improved glycemic control and decreased rates of hypoglycemia within the hospital setting.

This requires a detailed protocol of how the devices is to be used in the RCT and that all clinical staff assigned to the patient be trained to follow the protocol (i.e., staff must be trained to use CGM as a patient care tool).

The Dexcom G6 protocol includes the following:

- 1) The treatment group will have the data displayed with alarms set for glucose measurements of
 - A. Threshold alarm CGM glucose < 100 mg/dL
 - B. The urgent low soon alert, indicated by 2 downward arrows on the device reading. (Blood sugar of 55 mg/dL in less than 20 minutes)
 - C. Urgent low system alarm set at CGM glucose < 55 mg/dL.
- 2) Definition of target range is CGM glucose 100 -180 mg/dL
- 3) Definition of hypoglycemia is CGM glucose < 70 mg/dL (2 consecutive CGM readings below threshold)
- 4) Definition of hyperglycemia is CGM glucose > 300 mg/dL (2 consecutive CGM readings above threshold)
- 5) Definition of Severe hypoglycemia (see below)

Severe Hypoglycemia: the event required assistance of another person due to altered consciousness, and required another person to actively administer carbohydrate, glucagon, or other resuscitative actions. This means that the subject was impaired cognitively to the point that he/she was unable to treat himself/herself, was unable to verbalize his/her needs, was incoherent, disoriented, and/or combative, or experienced seizure or coma. These episodes may be associated with sufficient neuroglycopenia to induce seizure or coma. If plasma glucose measurements are not available during such an event, neurological recovery attributable to the restoration of plasma glucose to normal is considered sufficient evidence that the event was induced by a low plasma glucose concentration.

Definition of severe hyperglycemia/DKA:

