Hyperglycemic events are classified as severe hyperglycemia or DKA if the following are present:

- Symptoms such as polyuria, polydipsia, nausea, or vomiting;
- Serum ketones $> 1.0 \text{ mmol/L}$ or large/moderate urine ketones;
- Either arterial blood pH < 7.30 or venous pH < 7.24 or serum bicarbonate < 15 ; and treatment provided in a health care facility

Research Blood Glucose Protocol will be followed at all times.

Research Blood Glucose Protocol:

i. If CGM $> 180 \text{ mg/dL}$, patient will receive usual care based on attending physician or advanced practice professional orders based on readings from AC and HS finger stick blood glucose readings. In other words, CGM readings will not be used for management of glucose levels $> 180 \text{ mg/dL}$. Physicians and Advanced Practice Professionals (APPs – includes nurse practitioners or physician assistants) will be educated on the fact that, to prevent the risk of insulin stacking, CGM glucose values should not be used to bolus insulin or dose insulin. Elevated CGM readings $> 180 \text{ mg/dL}$ should not be relayed to on-call physicians or APPs by nursing staff. Pharmacy personnel will also be educated to not use CGM readings for dosing of insulin in order to prevent insulin stacking.

ii. If CGM 100-180 mg/dL with arrow direction  : continue usual care

iii. If CGM 100-180 mg/dL with arrow direction  : Recheck CGM in 1 hour; continue usual care

iv. If CGM 100-180 mg/dL with arrow direction  : Recheck CGM in 30 min; continue usual care

v. If CGM 100-180 mg/dL with arrow direction  (double arrow down): Recheck CGM in 15 min; continue usual care

vi. If CGM between 70-100 mg/dL and arrow direction  or  : continue usual care

vii. If CGM between 70-100 mg/dL and arrow direction  (horizontal) Recheck CGM in 30 min and follow research blood glucose protocol

viii. If CGM between 70-100 mg/dL and arrow  : Recheck CGM in 15 min and follow research blood glucose protocol

ix. If CGM between 70-100 mg/dL and arrow direction  (1 arrow down) Administer one of the following options and recheck CGM device 15 minutes after intervention and follow research blood glucose protocol again:

1. 2 oz. (60 ml) juice
2. 2 glucose tablets
3. 1/2 tube glucose gel

4. 12.5 ml D50W IV

x. If CGM between 70-100 mg/dL and arrow direction  (2 arrows down)

Administer one of the following options and recheck CGM device 15 minutes after intervention and follow research blood glucose protocol again:

1. 4 oz. (120 ml) juice

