2. 4 glucose tablets
3. 1 tube glucose gel
4. 25 ml D50W IV

xi. If CGM < 70 mg/dL: confirm with finger stick blood glucose and initiate standard of care per hospital hypoglycemia protocol per hospital policy. Resume CGM study research blood glucose protocol after two hours.

Additional standing orders in the Dexcom G6 protocol:

- a. Protocol will not encompass changes in basal, pre-meal, or corrective factor insulin ordered by the attending physician.
- b. Provide 24-hour CGM printout of glucose monitoring on morning rounds to the physicians caring for patients in the treatment group for their consideration in adjusting the scheduled basal/bolus insulin based on the CGM pattern. Information will also be provided regarding any interventions that were provided to the patient as a result of the research glucose protocol during the prior 24 hours.
- c. Review 24-hour CGM printout with patient in the treatment group to outline the effect of food, insulin and any exercise that may have occurred during the past 24 hours on glycemic control.

Usual Care for Glucose Control (Control Group): Patients assigned to the control group and wearing the Dexcom G6 PRO, will receive usual care as ordered by their attending physician. That means, the patient's glucose management will be based on reading from the blood glucose test that are conducted within a 24-hour period, and orders for glucose management will be determined by the attending physician.

Outcome Measures: Impact of CGM on key patient health indicators will be tracked during the enrolled patient's inpatient stay for up to 10 days. Number of events or amount of time will be calculated in consideration by the total time while the patient is hospitalized with an active Dexcom device (i.e., total time in which the Dexcom device is in use will serve as the denominator). Patients with less than 48 hours of Dexcom device reading will be excluded from outcome data analyses. Key outcomes abstracted from the Dexcom device will include:

- 1) Episodes of hypoglycemia (two consecutive CGM reading above or below threshold)
- 2) Episodes of hyperglycemia (two consecutive CGM reading above or below threshold)
- 3) Episodes of severe hypoglycemia
- 4) Episodes of severe hyperglycemia/DKA
- 5) Total time spent in the target range of 100-180
- 6) Number of times that CGM readings would change management of hypoglycemia compared to standard care

Other outcome measures to be collected include:

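### The severe hyperglycemia/DKA outcome is in effect DKA only, so a nonketotic hyperosmolar event that can end participation is never classed as severe hyperglycemia

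*Protocol*

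**What the plan says.** The Outcome Measures section of the Protocol lists "Episodes of severe hyperglycemia/DKA" as key outcome 4. The definition is introduced with "Hyperglycemic events are classified as severe hyperglycemia or DKA if the following are present". Three bullets follow: symptoms; raised serum ketones "or large/moderate urine ketones"; and "Either arterial blood pH < 7.30 or venous pH < 7.24 or serum bicarbonate < 15", together with treatment in a health care facility.

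The list of criteria for discontinuing individual participants has as item 4 "One DKA event or one episode of hyperglycemic, hyperosmolar nonketotic syndrome (HHNS". HHNS is thus named separately from DKA. It appears in no outcome list and not in Table 1.

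Under Reportable Adverse Events, item 5 covers "Diabetic ketoacidosis (DKA) as defined below (#4" and then, where there is no DKA, a hyperglycemic or ketosis event that meets criteria said to be given further on.

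Ordinary hyperglycemia is a separate outcome, key outcome 2: "Episodes of hyperglycemia (two consecutive CGM reading above or below threshold". Its threshold is item 4 of the Dexcom G6 protocol list: "Definition of hyperglycemia is CGM glucose > 300 mg/dL (2 consecutive CGM readings above threshold".

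Patients with under 48 hours of device readings are left out of outcome analyses (Outcome Measures and Subject Withdrawal). The Combined protocol and SAP reads the same on all these points, except that its DKA pointer is #5 instead of #4.

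**The concern.** The outcome's label promises two kinds of event and its criteria describe one. The protocol itself recognises a second serious hyperglycemic event, HHNS, but the outcome that should record such events has no place for it. Reportable event 5 appears to allow for a non-DKA event, but refers to criteria that are not supplied.

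What is at stake is the reading of a safety result. Fewer severe hyperglycemic events is listed among the anticipated benefits for the treatment group. A comparison on outcome 4 as defined would speak only to DKA, while its label would suggest that it covers severe hyperglycemia in general. Separately, the 48-hour rule can remove the very patients whose participation ended because of a severe event, whether DKA or HHNS.

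**Working it through.** No sample-size, power or event-rate figure in the documents bears on this point, so the check sets the definitions side by side and follows each type of event through them.

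**Step 1: how the definition reads.** The bullets are joined by semicolons, the last adds a further condition with *and*, and nothing says that any one item is enough. The natural reading is that all are required. The alternative, that any one suffices, would class a hyperglycemic event with nausea alone as severe, which cannot be meant.

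**Step 2: whether HHNS can meet it.** The documents give no criteria for HHNS but name it as nonketotic. On that name it fails the ketone item, and that is enough to fail the definition. The acidosis item is a further obstacle unless acidosis is present for another reason.

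**Step 3: where each event is recorded.**

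| Place in the plan | DKA | HHNS |
|---|---|---|
| Key outcome 4, severe hyperglycemia/DKA | Counted, subject to the 48-hour rule | Not counted |
| Key outcome 2, hyperglycemia | Counted if two consecutive readings exceed 300 mg/dL, subject to the 48-hour rule | Same, and not distinguished from any other excursion |
| Key outcome 5, time in 100-180 mg/dL | Lowers it while readings are out of range, subject to the 48-hour rule | Same |
| Discontinuation item 4 | Named | Named |
| Report to the IRB as a withdrawal, within 3 days | Yes, if withdrawn | Yes, if withdrawn |
| Report as an SAE | If serious | If serious |
| Reportable event 5 | Named | Not named; the non-DKA criteria it cites are missing |

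**Step 4: the 48-hour rule.** If either event ends participation before 48 hours of readings, the patient leaves all outcome analyses. This does not come from the ketone requirement and affects DKA equally. It matters here because the event itself can be what cuts the readings short.

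**Step 5: the pointers.** In the Protocol, item 4 of the numbered list is CGM glucose above 300 mg/dL. In the Combined protocol and SAP, item 5 is severe hypoglycemia. The severe hyperglycemia/DKA definition follows the list under its own unnumbered title. Neither pointer matches it.

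**Step 6: data source.** Outcome 4 is listed among those abstracted from the Dexcom device, which cannot supply symptoms, ketones, pH or bicarbonate. Table 1 lists neither those variables nor the outcome. The discontinuation and SAE records are where such events would be found.

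**Scale.** With 40 patients randomised 1:1, the planned arm is 40 / 2 = 20, so one patient is 1 / 20 = 5% of an arm. The expected number of unclassified events cannot be computed, because the documents give no DKA or HHNS rate.

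**The case against.** The strongest reply is that little is lost. With an active sensor and at least 48 hours of readings, an HHNS event that takes glucose above 300 mg/dL on two consecutive readings is counted under outcome 2, and it reduces time in range. A withdrawal for HHNS goes to the IRB within 3 days, and all SAEs are reported whatever their expectedness or relation to the study. That stands. A reader might infer from the definition that HHNS would appear in no outcome at all; the documents do not support this. What is missing is its classification as severe.

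A second reply is that the pointers are stale numbering. That also stands. A reader might infer that pointer #4, taken literally, makes every reading above 300 mg/dL reportable, and so makes reporting differ between arms because staff see the readings only in the treatment arm. This is speculative. A definition carrying DKA in its title follows the list, anyone looking for DKA would use it, and the two documents' pointers disagree with each other. Some list numbers may also have been lost when the text was extracted. This is a cross-reference to correct, not evidence of bias.

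Third, the treatment group's carbohydrate steps apply at CGM values of 70-100 mg/dL, above the protocol's own hypoglycemia threshold of 70, and a reader might infer a particular risk of hyperosmolar events. The documents draw no such link, and the point does not need it.

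Finally, the 48-hour exclusion is a separate rule. True, but outcome 4 cannot be reported completely unless it is addressed there.

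**Conclusion.** The point holds in a limited form. As written, outcome 4 counts DKA only. An HHNS event is never counted as severe hyperglycemia, although the protocol treats it as grounds for ending participation. Either event is lost from the outcome analyses if it ends participation before 48 hours of readings. Reportable event 5 cites non-DKA criteria that are not supplied.

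The size is small. Few or no events are likely in 40 patients, though that is a judgement and not a figure from the documents. The two outcomes named for the primary comparison, hypoglycemic events and time in range, do not depend on how a hyperglycemic event is labelled. The conclusion rests on two assumptions: that all elements of the definition are required, and that an event called nonketotic does not meet the ketone item.

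**What to change.** Report DKA and HHNS on separate lines under key outcome 4, by arm, in all randomised patients regardless of the 48-hour rule, with events taken from the discontinuation and SAE records instead of the device. In both documents, reconcile reportable event 5, discontinuation item 4, the severe hyperglycemia/DKA definition and the outcome list, so that the same events are named throughout, and correct the #4 and #5 pointers. The clinical criteria for each event, including those missing for non-DKA events, are for the investigators to set.

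The cost is a set of linked wording edits in two documents. No new data collection is needed to identify an event, because HHNS is already a discontinuation reason. The one drawback is that outcome 4 would use a different analysis population from the sensor-based outcomes, and the tables should say so.

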- 1) Test the health impact of CGM of inpatients as defined by rates of hypo- and hyperglycemia and the derivative of time in appropriate glucose range. Forty (40) patients will be randomized 1:1 into one of two groups. In the treatment group, patients will receive a Dexcom G6 device and the clinical staff (i.e., nursing and medical staff assigned to the patient's care) will be trained to use readings from the Dexcom G6 for the management of the patient's glucose levels below 100. In the control group, patients will receive a Dexcom G6 PRO device, but the clinical staff (i.e., nursing and medical staff assigned to the patient's care) will not have access to the readings and will provide usual care (four glucose checks per 24 hours and use of insulin or other diabetic agent ordered by the admitting and rounding providers to determine glucose management).
 - a. Hypothesis 1: Patients in the treatment group will experience fewer episodes of hypoglycemia as compared to patients in the control group as measured by the Dexcom device readings.
 - b. Hypothesis 2: Patients in the treatment group will experience less frequent hyperglycemia events as compared to patients in the control condition as measured by the Dexcom device readings.

Approach

Subject Recruitment & Enrollment Plan: Non-surgical, non-ICU patients with diabetes admitted to BSWMC-Temple who meet the inclusion/exclusion criteria delineated below will be approached for enrollment within 24 hours of admission. Screening and enrollment will be conducted by a research nurse or a Clinical Research Coordinator with consents signed for those wanting to participate.

Inclusion Criteria:

- Patients with Type 1 and Type 2 diabetes.
- Subjects 18 years of age or older with diabetes.
- Subjects willing to avoid using high dose acetaminophen (defined as greater than 4 gm per day)
- Subjects with expected hospital length-of-stay of 2 or more days.

- Subjects willing to wear CGM device.

Exclusion Criteria:

- Female subjects who are pregnant or lactating at the time of enrollment into the study. Females with childbearing potential will be queried about the possibility of pregnancy and a serum pregnancy test will be performed.
- Subjects with greater than 4gm use of Tylenol/24 hr.
- Surgical patients or patients with pre-planned surgery during the study.
- Subjects with acute illness admitted to the ICU or expected to require admission to the ICU.
- Patients who may potentially require IV insulin.

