Following randomization, the clinical nurse researcher will return to the patient's bedside to apply the Dexcom G6 or Dexcom G6 PRO sensor and transmitter. The sensor can be placed on the upper arm or abdomen. Those in the treatment group will then link the transmitter to the receiver. All clinical nurse researchers assigned to this project will be trained on the application of the device according to Dexcom protocol. The clinical nurse researcher will calibrate the device according to Dexcom protocol.

In some cases, patients will experience care procedures that require the device to be temporarily or permanently removed. If a patient requires a CT, the device will remain in place. If a patient requires an MRI as part of routine evaluation during hospitalization, the CGM device will be removed prior to imaging and a new one will be placed within twelve hours of the patient returning to their patient room on the nursing floor.

Dexcom sensors may be worn up to 10 days. The sensor will only be replaced if it is not providing appropriate readings or as noted above.

Standing Order for All Patients Enrolled in the Study:

Attending and/or consulting physicians will be responsible for writing orders for finger stick glucose measurements on all patients per standard care whether they are in the treatment or control group. Insulin orders will be determined by the patients' home medication history and current clinical status. To avoid investigator bias, orders written by the attending will not be adjusted by the study team with the exception of standing orders for nurse response to CGM readings as detailed below for those patients randomized to the treatment group. Standing orders for blood sugars <100 will allow for administration of glucose replacement in the treatment group based on Dexcom G6 reading.

CGM informed Clinical Care (Treatment Group):

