- 1) Questionnaires regarding perceptions of use of CGM devices in the inpatient setting to be completed by nurses and physicians
- 2) Questionnaires about the anticipated experience and actual experience of wearing a CGM device by the patient. To be administrated by a clinical research nurse or research Clinical Research Coordinator immediately prior to application of the device and immediately after removal of the final device applied (i.e., immediately prior to discharge)
- 3) Length of stay
- 4) The Diabetes Treatment satisfaction questionnaire-change (DTSQc) at completion of Dexcom data collection (11)

Other variables to be collected and entered in the data analyses include:

- 1) Patient demographics
- 2) Medical history
- 3) Admitting diagnosis
- 4) Information about home diabetic regimen
- 5) Most recent hemoglobin A1c found in EHR
- 6) Length of time since diagnosis of diabetes
- 7) Any skin irritation at the site of monitor device insertion

Data Analysis: The proposed inpatient health indicators related to glucose management will serve as the study's primary outcomes. The primary outcome measures, number of hypoglycemic events and time in the target range, will be compared between two groups using t-test. Non-parametric test (such as Wilcoxon-Mann-Whitney test) will also be used to examine unadjusted differences in the events between two groups if the distributional assumption of outcome measures does not meet the normality assumption. Other compounding variables such as patient demographics, admitting diagnosis, HbA1c will be adjusted where applicable. Statistical analyses will be conducted using SAS 9.2.

Other outcome measures on patient and provider's experience and perception of using CGM device and Diabetes Treatment Satisfaction Questionnaire-change (DTSQc) also will be analyzed. (See survey questions as stand-alone documents).

Anticipated Challenges: The study team composed of clinical staff and research members is well prepared to carry out the proposed research. There are, however, potential challenges to completing the proposed research. The team is aware of these challenges and will be prepared to address challenges if they emerge. Potential challenges include:

1. Potential adverse effects of the device
 - a) Skin irritation, infections, bleeding etc.
 - b) Inaccurate sensor value
 - c) Error in entering the calibration code from the sensor that would require manual calibration
 - d) Patient annoyance due to device alarms

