2. Clinical staff adherence to protocol
 - a) Nursing staff on the units will be trained in using Dexcom G6 readings for treatment group patients. Specific components that will be addressed include:

- During 2 hr warm up nursing staff will use finger stick blood glucose for dosing decisions.
- In situations when the CGM is not showing a number value or arrow, a finger stick blood glucose reading should be obtained.
- If patient symptoms do not correlate with CGM glucose values or if symptoms are indicative of hypoglycemia or hyperglycemia, a reading from the blood glucose meter will be obtained.
- Patients and caregivers should avoid the use of skin care products coming into contact with the Dexcom G6 device.
- Patients, caregivers, and nurses should be aware that the transmitter and display device should be kept within 20 feet with no obstacles like walls or metal separating the patient location from the device location.
- Patients who receive Tylenol, over the recommended dose of 1000 mg/6 hrs will require a finger stick blood glucose .

b) Attending physician on the units will be trained in using Dexcom G6 readings for treatment group patients

3. Recording of CGM data for data analyses

4. Removal and replacement of CGM sensor to accommodate patients receiving MRI.

If, as we assume, CGM is found to be a feasible practice for hospitalized patients, the team is prepared to move CGM into a practice innovation on the two units that participated in the pilot RCT. This will require further development of the RCT protocols into practice guidelines and ongoing training and monitoring of clinical staff implementation of CGM.

Anticipated benefits:

1. Treatment group
 - a. Improved glucose control in the target range of 100-180 mg/dL
 - b. Decreased severe hypoglycemic events
 - c. Decreased severe hyperglycemic events
 - d. Improved understanding of the trend of glucose readings over a 24-hour period and how these readings are affected by food, glucose, activity and stress
2. Control group
 - a. Realization of the patient's personal contribution to possibly improve medical practices for the larger population of inpatient patients with diabetes
 - b. Being allowed the experience of wearing a CGM device which may allow them to determine their personal interest in the use of such a device as an outpatient

Human Subjects:

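### Randomised patients with under 48 h of CGM readings are dropped from the outcome analyses, no all-patient analysis is planned, and the 2-day entry criterion does not secure 48 h

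*Protocol*

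**What the plan says.** The Protocol, under Outcome Measures, states: "Patients with less than 48 hours of Dexcom device reading will be excluded from outcome data analyses". The sentence recurs almost unchanged under Subject Withdrawal, and in the same two sections of the Combined protocol and SAP.

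Five other statements bear on it, all in the Protocol:

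- Inclusion Criteria: "Subjects with expected hospital length-of-stay of 2 or more days".
- Subject Recruitment & Enrollment Plan: eligible patients "will be approached for enrollment within 24 hours of admission".
- Application of the Dexcom Devices: "Following randomization, the clinical nurse researcher will return" to apply the sensor. For an MRI, "the CGM device will be removed prior to imaging and a new one will be placed within twelve hours of the patient returning".
- Anticipated Challenges, item 2a: "During 2 hr warm up nursing staff will use finger stick blood glucose for dosing decisions".
- Outcome Measures, on events and time in range: "total time in which the Dexcom device is in use will serve as the denominator".

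Among the other outcome measures, item 3 is "Length of stay". The Data Analysis sections name a t-test, a Wilcoxon-Mann-Whitney test, covariate adjustment where applicable, descriptive statistics and exploratory survey analyses. They name no as-randomised set, sensitivity analysis, missing-data method, or report of exclusions by arm.

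**The concern.** The rule selects patients on something that happens after allocation. Wear time is cut short by discharge, by discontinuation (the listed reasons include a severe hypoglycemic event, DKA, ICU transfer, and CGM lows that disagree with the finger stick) and by device removal. Length of stay, one of the determinants, is itself an outcome of the trial. Once patients are removed on such grounds, the two groups compared are no longer the two groups randomised.

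Both primary outcomes, the number of hypoglycemic events and time in target range, would be compared only in this subset. The background section calls the trial a feasibility pilot, but also says its findings will be used to determine the effect of CGM. A minimum-wear rule is a recognisable data-quality choice. The weakness is that it defines the only planned analysis, and that the entry criterion can admit patients who cannot satisfy it.

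**Working it through.** **1. Can a patient who meets the entry criterion reach 48 h of readings?**

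Inputs from the Protocol: expected stay of at least 2 days, read here as 48 h (the criterion is not defined in hours); approach 0 to 24 h after admission; 2 h warm-up; only in-hospital time with an active device counts.

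Hours of readings = stay − delay to placement − 2.

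- 48 h stay, sensor at admission: 48 − 0 − 2 = 46 h.
- 48 h stay, sensor at 12 h: 48 − 12 − 2 = 34 h.
- 48 h stay, sensor at 24 h: 48 − 24 − 2 = 22 h.
- 72 h stay, sensor at 24 h: 72 − 24 − 2 = 46 h.

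Stay needed = 48 + delay + 2, which is 50 h (delay 0), 62 h (delay 12) or 74 h (delay 24). It is longer if the sensor follows the approach by some hours. One MRI with the full twelve-hour gap and a new warm-up adds 12 + 2 = 14 h, giving 64 to 88 h. If warm-up time were counted as readings, any delay in placement would still leave a 48 h stay short.

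**2. How many would be excluded?**

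The documents give no length-of-stay distribution, so this step rests on assumptions: log-normal stays, stays below a floor dropped, placement uniform from 4 to 24 h, readings capped at 240 h (10 days), 2,000,000 simulated stays per scenario. Share with under 48 h of readings:

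| Median stay | log SD 0.6, floor 36 h | log SD 0.6, floor 48 h |
|---|---|---|
| 60 h | 43% | 29% |
| 72 h | 34% | 23% |
| 96 h | 21% | 14% |
| 120 h | 13% | 9% |

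With log SD 0.3 and floor 36 h, the share is 56% at median 60 h and 2% at 120 h. Of 40 randomised, that leaves 40 × 0.44 ≈ 18 to 40 × 0.98 ≈ 39. The range reflects the assumptions tried and is not a finding about this hospital.

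**3. Can the direction of bias be fixed?**

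Suppose there is no true effect, with 30% of patients at 1.0 event per day and 70% at 0.2. If a share e of the high-rate patients is excluded, the arm mean is (0.3(1 − e) × 1.0 + 0.7 × 0.2) / (0.3(1 − e) + 0.7).

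- e = 0.4: 0.32 / 0.88 = 0.364.
- e = 0.2: 0.38 / 0.94 = 0.404.

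Excluding 40% in the treatment arm and 20% in control gives a rate ratio of 0.364 / 0.404 = 0.90. The reverse gives 1.11, and equal exclusion gives 1.00. Either direction, or none, is possible.

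**4. What does keeping short traces cost?**

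One episode is 24/48 = 0.5 per day in 48 h of readings, 24/22 = 1.1 in 22 h, and 24/2 = 12 in 2 h. In the log SD 0.6 scenarios of step 2, the restricted standard error ran from 6% smaller to 32% larger than the all-patient one in an unweighted comparison. The first end has all variance within patients, the second all variance between patients. Those scenarios contain no trace under 10 h (36 − 24 − 2). If 5% of patients (2 of 40, assumed) stop at 1 to 12 h and all variance is within patients, the unweighted all-patient standard error is 16% (median 60 h) to 42% (median 120 h) larger than the restricted one (log SD 0.6, floor 36 h). An all-patient analysis therefore needs weighting by hours, or an offset.

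**The case against.** The strongest defence is that this is a 40-patient feasibility pilot with no stated power, that minimum wear is an ordinary quality rule, and that very short traces could swamp an unweighted test. The last part stands, as step 4 shows. It argues for weighting and for keeping the 48 h analysis, but it does not justify having no all-patient analysis. In a feasibility study early device loss is itself a result.

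It is also fair that the entry criterion is a minimum, stated as an expected stay and not in hours. The mismatch bites only near that minimum, and how often is unknown.

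Four stronger inferences are tempting, and the documents do not support them:

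- *The exclusion favours CGM.* Finger-stick confirmation of a low reading is specified only for the treatment arm, and control staff cannot see readings. Discontinuation for discordant lows might therefore act unequally. Nothing shows how often it would, and listing length of stay as an outcome does not show that CGM changes it.
- *A known share of patients will be lost.* Every percentage in step 2 depends on an assumed stay distribution.
- *Severe events vanish from the trial.* Severe hypoglycemia and DKA are reportable whatever the wear time. Discontinuation is permitted, not automatic, and may stop study treatment alone. The rule does not say whether it covers clinically defined events, and no test is named for them. What is missing is a planned count by arm in everyone randomised.
- *Analysing everyone gains precision.* It may gain or lose, depending on how variance divides between and within patients.

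**Conclusion.** The point holds, and the plan should be changed. As written, the only outcome comparison is in patients selected by post-randomisation wear time, with nothing planned to show the effect of that selection. The firm figures come from the protocol's own timings: a 48 h stay gives 46 h of readings at best and 22 h with placement at 24 h, against a stay of 50 to 74 h needed. They rest on reading 2 days as 48 h.

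The number excluded and the size and direction of any bias remain undetermined. The case rests on selection and on making it visible, not on power.

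**What to change.** In Outcome Measures and Subject Withdrawal of both documents, add text such as:

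> All randomised patients with any CGM readings are analysed in the arm assigned, over device time and weighted by hours of readings (for events, a count model with log device hours as offset may be used). This is reported beside the analysis restricted to 48 hours or more of readings. No conclusion is drawn from the restricted analysis alone.

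> Severe hypoglycemia and severe hyperglycemia/DKA are counted by arm in all randomised patients from the adverse-event reports.

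> The numbers with no readings and with under 48 hours are reported by arm and reason.

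The planned tests can stay for the restricted analysis. No new data are needed: device time is already the denominator, and the adverse-event sections already require the reports.

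The cost is a little more analysis work. Short traces stay noisy, which is why weighting or an offset is part of the change and not an option. Hours-weighting gives long stays more influence, so the two analyses should be read together. Patients with no readings remain outside the CGM comparison, so the added analysis reduces the selection without removing it.
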